## SYNOPSIS

Study Title	A Prospective, Multicenter, Randomized Controlled Study to Evaluate the Effect of Absorbable Adhesion Barrier in Preventing the Abdominal Incision Adhesions
Study Objectives	The primary objective of this study is to evaluate the efficacy and safety of INTERCEED™ Absorbable Adhesion Barrier (hereafter called INTERCEED™) in reducing the incidence of adhesions at the abdominal incision site in patients undergoing laparoscopic colorectal surgery.
Number of Study Sites	12 Sites
Number of Subjects	220 Subjects
Study Design	
This is a prospective, randomized controlled study. The study population will include 220 subjects scheduled to undergo laparoscopic radical resection of rectal carcinoma with preventive ileostomy (Phase 1 operation).
 
During the Phase 1 operation, when the definite decision to create a temporary ostomy is made, patients will be randomized in 1:1 ratio to either the treatment arm (INTERCEED™) or the control arm (standard of care treatment: no adhesion barrier, no placebo). In subjects assigned to the treatment arm, the INTERCEED™ must be applied beneath the target incision site (the midline incision mainly for the removal specimen).
 
The subjects will return 3-9 months after the phase 1 operation (colorectal resection with temporary ileostomy) for phase 2 operation, to have their diverting ostomy taken down (ileostomy reversal).
 
During the phase 2 operation (ileostomy reversal), the incidence, extent and severity of adhesions will be evaluated through the laparoscope.
 
An ad-hoc interim analysis is proposed based on feedback received from the investigators who observed very low rate of adhesions at the second procedure for ostomy reversal. The ad-hoc interim analysis is planned to be performed while at least 61% of the total number of participants with evaluable primary endpoints

	
are available. If the conditional power (CP) is <math>\leq 60\%</math>, the observed adhesion rate difference magnitude is much less than the assumed difference magnitude of 0.25, therefore, the study will be terminated due to low adhesion rate and small effect size between INTERCEED and control arms. Otherwise, the study will continue until the study completion as planned.

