### **13. REGULATIONS OF ADVERSE EVENT AND DEVICE DEFECT REPORTING**

#### **13.1. Adverse event**

An AE is defined as any untoward medical occurrence in the process of clinical trial, regardless of its relationship to the investigational medical device.

The investigator should determine whether an AE occurs and determine its relationship to the study device or surgery at each evaluation for the subjects recruited for the clinical study.

All AEs, study device faults and other product problems must be recorded in the medical record and entered in the CRF. All AEs need to be recorded in the EDC system in 2 weeks.

Postoperative pain, fever and laboratory abnormalities is expected and will not be documented as an adverse event unless the Investigator considers the pain or fever to exceed that normally anticipated following the surgery or related to study devices. Also, the adverse event, not including the serious adverse event and ileus event, which is "not relative" or "unlikely related" to the study device and occurred 1. between 30 days after Phase 1 operation and the hospitalization for Phase 2 operation or 2. between Visit 6 and Visit 7 should not be documented.

The severity of adverse event is graded into the following levels:

**Mild:** Existing signs or symptoms have no impact on the usual activities of the subjects, or transient, no treatment required, with no sequel.

**Moderate:** Have an impact on the usual activities of the subjects, with no interference, with possible need of treatment.

**Severe:** Cause the symptom of severe discomfort, resulting in major impact on the usual activities of the subjects, medical intervention or treatment required.

The causal relationship of adverse events should be determined as follows:

**Not related:** The event is definitely not related to the use of product

**Unlikely related:** The time sequence between the use of product and the event shows that the event is unlikely associated,

**Possibly related:** The time sequence between the use of product and the event shows that the event is likely associated, or AE may also be caused by the disease or concomitant treatment of the subjects,

**Probably related:** The time sequence shows the event has temporal relationship to the use of investigational product, or the event is alleviated at the end of use of product, or it is unable to give reasonable explanation to this event according to the disease of the patient,

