### **20.2. Responsibilities of Clinical Trial Institution and Investigator**

- 1) The clinical trial institution should evaluate the relevant resources according to the features of investigational medical device prior to the clinical trial, so as to decide whether to perform this clinical trial.
- 2) The clinical trial institution should properly keep the records and documents of clinical trial according to the agreement with the sponsor.

- 3) Make sure that the investigators responsible for the clinical trial should have the qualification in accordance with the requirements of related laws and regulations.
- 4) The administrative department for clinical trial of medical device of clinical trial institution should cooperate with the sponsor to apply to the Ethics Committee and submit the relevant documents prior to the clinical trial according to requirements.
- 5) The investigator should ensure that the relevant workers participating in the trial have the enough resources and proper training, and keep the training related documents.
- 6) The investigator should ensure to use the investigational medical device only for the subjects of this clinical trial, and may not charge any fee.
- 7) The investigator should strictly follow the clinical trial protocol, with the exception of emergency circumstances when the subject faces the direct risk and needs immediate clinical measures, which can be reported later in a written form.
- 8) The investigator is responsible for recruiting the subjects, communicating with the subject or its legal representative before signing the informed consent.
- 9) The investigator should protect the rights, safety and health of the subjects.
- 10) In case of adverse event occurring in the clinical trial, the investigator should protect the safety of the subjects and timely report the event to the regulatory authority.
- 11) The investigator should record all adverse events occurring and device defects found in the process of clinical trial, work with the sponsor to analyze the causes of the events, form the written analysis report, present the comments on the continuation, discontinuation or termination of the trial, and report to the Ethics Committee by the administrative department for clinical trial of medical device of clinical trial institution for review.
- 12) The investigator should make sure that the clinical trial data is accurately, completely, clearly and timely recorded in the Case Report Form.

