3.4.1 Adverse events

All adverse events (AEs) will be summarized, and the AEs will be coded using the MedDRA 23.1 dictionary.

An adverse event refers to any detrimental medical events in the course of a clinical trial, whether or not related to the investigational medical device. All AEs, study device failure, and other product problems must be documented in the medical record since the signing of informed consent. In the meantime, for non-serious AEs (excluding ileus-related events) that occur during the period from 30 days after the phase 1 operation to the second hospital admission before the phase 2 operation specified in the protocol, or between Visit 6 and Visit 7, recording and collection are not required if they are assessed as not related or unlikely related to the study device by the study doctor.

The incidences of AEs will be summarized per treatment group and in total using the number of cases (percentage). During the summary of number of cases per PT, if a subject experienced the same AE (distinguished per PT) repeatedly, he/she will be counted once only when calculating the number of cases; During the summary per severity of AE, for the same AE of different severity, the most severe one will be counted when calculating the number of cases.

According to the rules above, the AEs will be summarized generally and per SOC and PT level, and the types of AEs are summarized as follows:

- All AEs recorded during the study period in the EDC
- AEs related to the study product/phase 1 operation/phase 2 operation (including: definitely related, probably related, possibly related, and unlikely related)
- SAE
- Serious AEs related to the study product/phase 1 operation/phase 2 operation (including: definitely related, probably related, possibly related, and unlikely related)

In addition, for AEs that have occurred at least once, the number of cases and percentage will be calculated per SOC, PT, and severity (mild, moderate, and severe), and the same analysis will also be performed for AEs related to the study product.

All AEs will be tabulated to record the AE name (PT), onset date, end date, severity of AE, SAE or not, classification of SAE, relevance with the study product, action taken, and outcome, etc., and the AEs/SAEs leading to death will be tabulated independently.

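### The Safety set as written contains no controls, although the SAP compares arms on it; separately, in restricted windows the by-arm AE table is not like for like

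*Protocol*

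**What the plan says.** **Safety set.** Protocol 8.9 and SAP 2.2 both confine the Safety set to subjects who received the study device. The control arm gets "no adhesion barrier, no placebo" (protocol Synopsis). SAP 3.4 places all safety analyses on this set, by treatment group according to actual treatment, with Wald intervals for experimental minus control in SSI, dehiscence and delayed healing. SAP 3.3.2 puts the secondary effectiveness endpoints on the same set: a chi-square test for mechanical ileus and Mantel-Haenszel tests for extent and severity of adhesions at the target incision. Protocol 8.1 and 8.9 and SAP 2.3.5 assign those endpoints to ITT, and SAP 2.2 assigns them to ITT and PP.

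**AE recording.** Protocol 13.1 opens with a general rule: "All AEs, study device faults and other product problems must be recorded in the medical record and entered in the CRF". It then excepts non-serious, non-ileus AEs rated not or unlikely related "to the study device and occurred 1. between 30 days after Phase 1 operation and the hospitalization for Phase 2 operation", or falling between Visits 6 and 7; these are not to be documented. For the same windows SAP 3.4.1 says that "recording and collection are not required if they are assessed as not related or unlikely related to the study device by the study doctor". Protocol 20.2 says: "The investigator should record all adverse events occurring and device defects found in the process of clinical trial". Protocol 13.3 asks only for the AEs that the protocol requires.

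**AE tables.** SAP 3.4.1 summarises by arm "All AEs recorded during the study period in the EDC", with no restriction to particular periods. It also provides a listing: "All AEs will be tabulated to record the AE name (PT), onset date, end date, severity of AE".

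**The concern.** Safety is part of the primary objective, and protocol 7.1.7 says safety data are compared between groups. Two separate features undermine that comparison.

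First, a Safety set made up of device recipients has no comparator. The planned differences for SSI, dehiscence and delayed healing cannot be computed on it, nor can the ileus and adhesion-grade tests in SAP 3.3.2.

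Second, once controls are added, the AE table still mixes periods in which both arms are recorded alike with periods in which recording turns on relatedness to a device that only one arm receives. The relatedness scale in protocol 13.1 is framed on use of the product, and no rule is given for a subject without it. The implanting surgeon is unblinded and no AE assessor is named as blinded. Applied literally, late non-serious, non-ileus AEs enter the database only from the INTERCEED arm. The by-arm difference in those windows would then reflect the recording rule as well as the patients.

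**Working it through.** The plan gives no figure on this point. The only planned numbers needed are the arm sizes: 77 evaluable per arm / (1 - 0.30) = 110 randomised per arm (protocol 8.2.1).

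**1. Safety set.** If every subject is treated as allocated, the set as written holds 110 INTERCEED subjects and 0 controls. A control given the device in error would enter the set but, under SAP 3.4, be grouped as INTERCEED. The control denominator is therefore 0 in every case. With all randomised subjects who had Phase 1 included, it is about 110 against 110.

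**2. Who has which window.**
- Window 1 runs from day 30 after Phase 1 to the Phase 2 admission. It applies to everyone who reaches Phase 2, at 3-9 months.
- Window 2 runs from Visit 6 to Visit 7. It exists only if Visit 6 falls at 3-6 months (flowchart footnote h), and it shrinks as Visit 6 approaches month 6.

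**3. Share of reporting time, for completers.** One month is taken as 30.44 days. Length of stay is not in the documents, so two cases are assumed:
- *3 days*: admitted on the day of Phase 2, Visit 6 at day 3.
- *17 days*: admitted 7 days before, Visit 6 at day 10.

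Share = (window 1 + window 2) / total time. For example, with Phase 2 at 3 months (91.3 days), Visit 7 at 6 months (182.6 days) and a 3-day stay: (91.3 - 30) + (182.6 - 94.3) = 149.6, and 149.6/182.6 = 81.9%. Counting from consent adds 14 days to the total.

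| Phase 2 / Visit 7 (months) | From Phase 1, 3 days | From Phase 1, 17 days | From consent, 3 days | From consent, 17 days |
|---|---|---|---|---|
| 3 / 6 | 149.6/182.6 = 81.9% | 135.6/182.6 = 74.3% | 76.1% | 69.0% |
| 3 / 7 | 180.1/213.1 = 84.5% | 166.1/213.1 = 77.9% | 79.3% | 73.1% |
| 6 / none | 152.6/185.6 = 82.2% | 145.6/192.6 = 75.6% | 76.5% | 70.5% |
| 9 / none | 244.0/277.0 = 88.1% | 237.0/284.0 = 83.4% | 83.8% | 79.5% |

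The range is 74-88% from Phase 1 and 69-84% from consent. Fully captured time after Phase 1 is 30 + 3 = 33 to 30 + 17 = 47 days.

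**4. What the filter could do (every value assumed).** Let b be the share of each arm already counted with an AE in the fully captured periods, r the true window risk, and s the share of INTERCEED window events rated possibly related or higher. Assume independence and no control event so rated. Then recorded difference = (1 - b) x r(INTERCEED) x s, and true difference = (1 - b) x (r(INTERCEED) - r(control)).
- Equal risks of 20%, s = 0-20%: b = 0.4 gives 0 to 0.6 x 0.20 x 0.20 = 2.4 points; b = 0.8 gives 0 to 0.8 points. The true difference is 0.
- Equal risks of 10-50%, s = 10-50%, windows alone (b = 0): 0.10 x 0.10 = 1 point to 0.50 x 0.50 = 25 points. The true difference is again 0.
- Risks 45% against 30%, s = 0-20%: b = 0.4 gives a true 9.0 points, recorded as 0-5.4; b = 0.8 gives a true 3.0, recorded as 0-1.8.

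The result depends almost wholly on s, which the documents do not give, and it can go either way.

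**The case against.** **The Safety set is a drafting slip.** SAP 3.4 groups by actual treatment and subtracts control from experimental, so controls are plainly meant to be included. That stands: a reader should not infer that the trial intends to go without a control safety column. But the definition, repeated in both documents, does not deliver the intent.

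**Few late events would be rated related.** Protocol 5.1.1 says the device, used as directed, is absorbed within four weeks, and window 1 opens at day 30. If s is near zero, the windows add almost nothing to either arm. This is a strong point. The documents do not give it as the reason for the rule, and they say the absorption rate varies, but it rules out any claim of a large false INTERCEED excess. In the 2.4-point illustration the effect is also small beside sampling error: at 110 per arm and AE proportions of 40-80%, the 95% half-width 1.96 x sqrt(2p(1 - p)/110) is about 11-13 points.

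**The scope is narrow.** SAEs and ileus are exempt. SSI, dehiscence and delayed healing are scheduled items at Visits 4-7 in both arms. The AE table is descriptive and a dated listing is planned. All of this stands.

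**Two stronger readings are tempting but unsupported.** One is that protocol 13.1 contradicts itself. It reads as a general rule followed by an exception, and protocol 13.3 supports that; the unharmonised text is in 20.2, along with the difference between a prohibition in 13.1 and an optional omission in SAP 3.4.1. The other is that SAP 3.4.1 is inconsistent in defining related AEs as "including: definitely related, probably related, possibly related, and unlikely related". That definition covers relation to the product or either operation, and events unlikely to be device-related remain recordable outside the windows. Showing them separately is a matter of presentation.

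**Conclusion.** The Safety set is wrong as written in both documents. It holds no controls, so the comparisons in SAP 3.4 cannot be carried out on it. SAP 3.3.2 compounds this by moving secondary effectiveness onto the same set, against the ITT specification elsewhere. This conclusion rests on the text alone.

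The AE windows are a lesser point, where a cheap improvement is available. Recording of late non-serious, non-ileus AEs depends on a link to a device that controls do not have, and how control events are to be rated is not stated. The by-arm table is therefore not like for like over about 69-88% of a completer's reporting time, given the assumed stay of 3-17 days. That is a share of time, not of events, and it is smaller for early withdrawals. A reader might infer a bias of known size against INTERCEED; the documents support neither a size nor a direction, and the effect may be small.

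**What to change.** 1. **Protocol 8.9 and SAP 2.2:** define the Safety set as all randomised subjects who underwent the Phase 1 operation, grouped by treatment actually received (INTERCEED or no barrier).
2. **SAP 3.3.2:** restore ITT for the secondary effectiveness endpoints.
3. **SAP 3.4.1:** base by-arm summaries of non-serious, non-ileus AEs on the equally captured periods: consent to day 30 after Phase 1, and Phase 2 admission to Visit 6, the latter with subjects reaching Phase 2 as denominator. Keep SAEs and ileus over all follow-up. Tabulate or list restricted-window AEs separately, without comparing arms.
4. **Protocol 13.1, 13.3 and 20.2 and SAP 3.4.1:** reconcile the instructions on which AEs are recorded.

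The cost is wording plus one table specification. AE onset dates are already to be listed. The Phase 2 admission date is also needed and the flowchart does not name it; if it is not in the database, starting the second period at the operation date stays within fully captured time. The downside is that later non-serious, non-ileus AEs are described but not compared by arm: that comparison then covers about 33-47 days after Phase 1, plus up to 14 days of screening. The second period also compares only subjects who reach Phase 2, so differential dropout before then would need to be reported beside it.

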### **13.2. Serious Adverse Event**

A Serious Adverse Event is any AE that results in a death or a serious deterioration in the health of the subject during the clinical trial, including a life-threatening illness or injury, a permanent impairment of a body structure or a body function, in-patient hospitalization or prolongation of existing hospitalization, medical or surgical intervention to prevent permanent impairment of a body structure or a body function; or results in fetal distress, fetal death or congenital abnormality, congenital anomaly, etc. The rehospitalization events after Phase 1 operation only for receiving the chemotherapy/radiotherapy which planned after the diagnosis of the primary disease will not be documented as an adverse event.

### **13.3. Device Defect**

The device defect is defined as unreasonable risk occurred under normal use of medical device during the clinical trial, which may do harm to the human health and life safety, such as label error, quality problem, fault, etc.

For the device defect that may cause serious adverse event, the sponsor should report to the CFDA and the competent department of health and family planning at the same level where the device is registered within 5 workdays after being informed. The sponsor should also inform other clinical trial institutions and investigators that participate the trial, and timely inform the Ethics Committee of such clinical trial institution through its administrative department for clinical trial of medical device. The investigator should record all adverse events required in protocol and device defects found in the process of clinical trial, work with the sponsor to analyze the causes of the events, form the written analysis report, present the comments on the continuation, discontinuation or termination of the trial, and report to the Ethics Committee by the administrative department for clinical trial of medical device of clinical trial institution for review.

### **13.4. Reporting Procedure, Contact Information**

The investigator should ensure to provide the sufficient treatment for Any adverse event of any

subjects, including the laboratory detection value with clinical significance and related to this study.

The adverse event is reported from the start of signing the informed consent to the end of the study of subjects. All adverse events should be followed up, until the adverse event is resolved, stable or the study is completed.

The investigator should record the nature, severity, treatment and outcome of serious adverse event, and determine whether it is related to the study device, drug administration or surgery specified in the study protocol. The investigator will report the adverse event to the sponsor via the Case Report Form (CRF).

The investigator must submit the serious adverse events occurred in the study and the device defects that may cause serious adverse event to the sponsor and the regulatory authorities at every level (or designated person) immediately after being informed of the event; if required by the sponsor, the further information should be provided.

All serious adverse events need to be followed up until the event is resolved (with or without sequela). When the event is not resolved or stable at the end of study, the medical monitor in this clinical study will decide whether it is necessary to collect the further follow-up information.

The investigator and sponsor should report the serious adverse events occurred in the study and the device defects that may cause serious adverse event to the regulatory authorities at every level according to the requirements of laws and regulations.

The study device with device defect should be returned to the sponsor according to the instructions given in Section 13.3 of this study. Once a device defect is found, the site should inform the sponsor as soon as possible, and report the device related information on the relevant CRF.

The contact person to report adverse event and device defect is as follows:

Adverse event: [contact]

Device defect: [contact]

## **14. DEVIATION FROM CLINICAL TRIAL PROTOCOL AND REGULATIONS FOR CLINICAL TRIAL PROTOCOL AMENDMENT**

The study protocol deviations are defined as the circumstances that fail to comply with the requirements of clinical trial protocol intentionally or unintentionally.

All protocol deviations should be reported as protocol deviations to the sponsor. The records include the date of and reason for protocol deviations. The investigator should also report the protocol deviations to the EC according to the procedures and in combination with the requirements and procedures of the EC.

If protocol amendment occurs, the sponsor or designated person should submit the change data of study protocol to the investigator, regulatory authority, and the Ethics Committee, etc. according to the relevant laws and regulations. All major amendments must be approved by the Ethics Committee and regulatory authority (if needed) prior to implementing any changes to study procedures.

If an amendment likely has major impact on the following items, this amendment belongs to the major amendment:

- Safety or physical or mental health of subjects;
- Scientific value of trial;
- Implementation or management of trial;
- Quality or safety of investigational medical device specified in the trial.

